# 11.3 Criteria for Stopping Study

We expect the safety profile to be similar for Cohort A and B so will evaluate the stopping rule in the combined cohort. The expected Grade 4 or 5 treatment related AE rate from gemcitabine with SBRT is approximately 6% (Herman ref), and we would consider a 10% rate in our study to be unacceptable. An interim safety analysis is planned after every six patients are accrued and followed for 1 year to assess Grade 4 or 5 treatment-related AEs. If 3 or more out of 6, 4 or more out of 12, 5 or more out of 18, or 6 or more out of 24 patients have a Grade 4 or 5 treatment-related AE within one year, accrual will be terminated. These stopping boundaries represent where the lower bound of a 90% exact binomial confidence interval would be in excess of 10%.

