# 11.5 Sample Size

It is anticipated that this study will last approximately 42 months (30 months of accrual and 12 months of additional follow-up while cohort matures). The total enrollment will be 38. With a 1 to 5 ratio of prior RT treatment to no prior RT treatment, we expect to enroll approximately 6 subjects in Cohort A and 30 in Cohort B. Six subjects in Cohort A will allow us to obtain only a preliminary sense of efficacy; however, we do not want to exclude this important cohort from the study since our focus is on safety. A sample size of 38 will allow us to estimate the primary outcome of acute (within 3 months of treatment) grade 3 or greater gastrointestinal and hematologic toxicity to within approximately 12% using a 90% exact confidence interval assuming the rate is similar to Herman et al. (28%).

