# 11.11 Interim Analysis

No interim analyses are planned other than assessing Grade 4 or 5 treatment-related AEs after every  $6^{\rm th}$  patient.

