#### 14. DATA AND SAFETY MONITORING PLAN

Investigators will conduct continuous review of data and patient safety. Monthly review meetings for moderate risk trials are required and will include the principal investigator, clinical research specialist and/or research nurse (other members per principal investigator's discretion). Monthly meeting summaries should include review of data, the number of patients, significant toxicities as described in the protocol, and responses observed. Summaries will be submitted and reviewed monthly by the IUSCC Data Safety Monitoring Committee (DSMC). Submit to [contact].

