#### 14.2 Early Study Closure

At any time during the conduct of the trial, if it is the opinion of the investigators that the risks (or benefits) to the patient warrant early closure of the study, this recommendation should be made in writing to the DSMC. Alternatively, the DSMC may

Protocol Version Date: 07/02/2024 Page 23

initiate suspension or early closure of the study based on its review of the investigator reports.

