# 15.3.2 Reporting to the IUSCC Data Safety Monitoring Committee (DSMC)

Regardless of study sponsorship, the study team must enter all initial and follow-up SAE, expedited, and noncompliance reports into OnCore® for review by the DSMC chair and/or coordinator. Expedited reports may include IRB Prompt Report Forms and additional SAE forms as required by the sponsor. When follow-up information is received, a follow-up report should also be created in OnCore®. This DSMC reporting requirement is **in addition to any other** regulatory bodies to be notified (i.e. IRB, FDA, pharmaceutical company, etc.). The DSMC chair and/or coordinator will review all SAE, expedited, and noncompliance reports monthly.

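### The only numeric stopping rule waits one year for each block of six, so at planned accrual its four looks come with about 21, 27, 33 and 38 of 38 patients already enrolled.

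*Combined protocol and SAP*

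**What the plan says.** Section 11.3 (Criteria for Stopping Study) pools the two cohorts and sets the timing: "An interim safety analysis is planned after every six patients are accrued and followed for 1 year". Accrual ends at 3 or more patients with an event out of 6, 4 or more out of 12, "5 or more out of 18, or 6 or more out of 24 patients". An event is a treatment-related Grade 4 or 5 AE within one year. The section expects a rate of about 6% and calls 10% unacceptable. Each boundary is set where the lower limit of a 90% exact binomial interval exceeds 10%.

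Section 11.5 (Sample Size) says "The total enrollment will be 38" and plans "30 months of accrual and 12 months of additional follow-up while cohort matures". Section 11.11 (Interim Analysis) says "No interim analyses are planned other than assessing Grade 4 or 5 treatment-related AEs after every" sixth patient, and does not mention the one-year wait.

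Other safeguards exist. Section 14 says "Monthly review meetings for moderate risk trials are required", with summaries going to the DSMC each month. Section 14.2 lets the investigators recommend closure ("At any time during the conduct of the trial, if it is the opinion of the investigators" that the risks warrant it) and lets the DSMC suspend or close the study itself. Section 15.3.2 adds "The DSMC chair and/or coordinator will review all SAE, expedited, and noncompliance reports monthly". None of these sections gives a numeric trigger, and no section holds accrual while a block matures.

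**The concern.** A rule whose only action is to end accrual protects patients only while there is accrual left to end. Here each look comes at least 12 months after the last patient of its block enters, and enrolment continues meanwhile at the planned rate of more than one patient a month. If the true Grade 4-5 rate were well above 10%, the pre-specified rule would act late or, at the fourth look, not at all. Earlier action would depend on unquantified judgement at the monthly reviews. This matters because Section 5 describes the trial as a study of safety.

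**Working it through.** **1. The plan's own boundaries.** The lower limit of the two-sided 90% Clopper-Pearson interval is the 5th percentile of Beta(x, n - x + 1).

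| n | Boundary x | Lower limit | Lower limit at x - 1 |
|---|---|---|---|
| 6 | 3 | 15.3% | 6.3% |
| 12 | 4 | 12.3% | 7.2% |
| 18 | 5 | 11.6% | 8.0% |
| 24 | 6 | 11.5% | 8.6% |
| 30 (not in plan) | 7 | 11.5% | 9.1% |
| 36 (not in plan) | 8 | 11.6% | 9.5% |

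The four published boundaries reproduce. The same criterion gives 7/30 and 8/36 if the rule is continued.

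**2. When the looks fall.** Inputs are 38 patients, accrual length A = 30 months (both Section 11.5) and a 12-month wait (Section 11.3). Uniform accrual is assumed, at 38/30 = 1.267 per month.

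- Look time = n × A/38 + 12.
- Enrolled at the look = min(38, n + 12 × 38/A) = min(38, n + 15.2).

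| Look | Month | Enrolled | Most that can be spared |
|---|---|---|---|
| 6 | 16.7 | 21.2 | about 17 |
| 12 | 21.5 | 27.2 | about 11 |
| 18 | 26.2 | 33.2 | about 5 |
| 24 | 30.9 | 38 | 0 |

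The fourth look coincides with the end of accrual when 24A/38 + 12 = A, so A = 12/(1 - 24/38) = 32.6 months. It can act only if accrual takes longer than that. At A = 36 it finds 24 + 12 × 38/36 = 36.7 enrolled and spares 1-2 patients. At A = 48 the four looks find 15.5, 21.5, 27.5 and 33.5. Looks at 30 and 36 patients with the wait would fall at months 35.7 and 40.4, too late to act.

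**3. Crossing probabilities.** These come from an exact binomial recursion over blocks of six. At a true 20% rate, for example, the first look crosses with probability 1 - (0.262 + 0.393 + 0.246) = 9.9%.

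| True rate | First three looks | Four boundaries | Six boundaries |
|---|---|---|---|
| 6% | 0.9% | 0.94% | 1.02% |
| 10% | 4.6% | 5.6% | 6.8% |
| 20% | 33.3% | 41.7% | 54.1% |
| 30% | 70.4% | 81.1% | 92.0% |

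Counting events as they occur does not alter the four-boundary column: the k-th event among the first n patients crosses whether it is counted at once or a year later. Only the date of action moves. At 30-month accrual the written rule can end enrolment only through its first three looks.

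**4. Patients enrolled.** This is a simulation with 100,000 runs per scenario and uniform accrual. The alternative uses six boundaries and acts at the end of the month in which one is reached. The documents give no event timing, so two cases are assumed: event times uniform over 3 months or over 12 months after entry.

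| Accrual, true rate | As written | Events within 3 months | Events over 12 months |
|---|---|---|---|
| 30 months, 10% | 37.5 | 36.7 | 37.1 |
| 30 months, 15% | 36.3 | 33.2 | 34.9 |
| 30 months, 20% | 34.4 | 27.9 | 31.4 |
| 30 months, 30% | 29.8 | 17.6 | 23.8 |
| 36 months, 20% | 33.2 | 27.7 | 30.6 |
| 36 months, 30% | 27.5 | 17.3 | 22.3 |

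The chance that accrual ends before 38 are enrolled (30 months) is 33% as written versus 52% or 44% at a true 20% rate, and 4.6% versus 6.4% or 5.6% at 10%. Repeat runs agree to within about 0.2 patient and one percentage point.

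**The case against.** The strongest reply is that the as-written column assumes nobody acts before the scheduled look. Monthly toxicity review and the power to close at any time make that unlikely at rates of 20-30%, where most of the gain lies. This stands as a limit on size: the differences are upper bounds on the benefit. It does not supply a trigger, and the fix attaches the plan's own thresholds to those same meetings.

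Reporting delay also reduces the gain. AE evaluations are scheduled at 4-6 weeks and then at 3, 6, 9 and 12 months, and visits after the first may take place elsewhere with a 30-day window (Section 9). With an assumed two-month lag, the gain at a true 20% rate is about 1.8 patients if events spread over 12 months and 5.1 if they fall within 3 months. It shrinks but remains.

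The gain is small near the expected rate: about 0.1 patient at 6% and under one at 10%. The fourth look also misses the end of accrual by only about a month, so slower accrual would revive it. Both points are correct.

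Finally, waiting for complete follow-up is a recognisable choice for a one-year endpoint, and Section 11.11 may simply be shorthand for Section 11.3. Neither is a computational error. But the one-year event window can be kept without the wait, and the Section 11.11 wording is a minor alignment point on which the conclusion does not rest.

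**Conclusion.** The concern holds and should be fixed. At the planned accrual rate the numeric rule first acts with 56% of patients enrolled (21.2/38), and its last boundary falls about one month after accrual ends. Removing the wait, with the two added boundaries, saves on average about 1.4 to 3.1 patients at a true 15% rate, 3.0 to 6.5 at 20% and 6.0 to 12.2 at 30%. These figures rest on uniform accrual over 30 months, the two assumed event timings, month-end action and no earlier action by judgement. Slower accrual, reporting delay or alert monthly review would reduce them. The boundaries themselves are correctly calculated; the fault is in when they are applied.

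**What to change.** Keep the four thresholds, the one-year event window and the stated action, and apply the thresholds as events occur. Suggested text for Section 11.3:

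> Accrual will end as soon as 3 of the first 6, 4 of the first 12, 5 of the first 18, 6 of the first 24, 7 of the first 30 or 8 of the first 36 treated patients have had a qualifying event (treatment-related, Grade 4 or 5, within one year), whether or not the remaining patients have completed one year. Counts are checked at each monthly review meeting.

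Section 11.11 should then refer to the Section 11.3 rule, so that both give one timing.

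The 7/30 and 8/36 boundaries are optional. Most of the gain comes from dropping the wait: at a true 20% rate with events within 3 months, mean enrolment is 28.5 without them and 27.9 with them.

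The cost is wording in two sections and the IRB approval that Section 13 requires for protocol changes. The monthly meetings already exist, and no new data, staff or patients are needed. With only the four boundaries, the crossing probability does not change. With all six it rises from 0.9% to 1.0% at the expected 6% rate and from 5.6% to 6.8% at 10%.

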#### 11.4 Analysis Datasets

- Enrolled Population The enrolled population consists of all patients who enroll in the study.
- Efficacy Population The efficacy population comprises all patients who meet
  the eligibility criteria, are registered onto the study, get at least one session of
  Linac-based SBRT, and have at least one follow-up evaluation. This set will be
  used for efficacy analysis.
- Safety Population The safety population comprises all patients who have received at least one session of Linac-based SBRT. This set will be used for safety analysis.

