# 7.3 Follow-Up

Following Linac-based SBRT, all patients will be monitored clinically and with serial imaging (CT scans and/or PET/CT if possible and as deemed necessary by the treating physician). A detailed medical history with physical examination and quality of life assessment will be performed at 4-6 weeks, 4 months, 6 months, 9 months and 1 year after radiation treatment. In years 2-5, the follow up interval will be every 3-6 months, as determined by the principal investigator. Follow up intervals may also be more frequent as indicated clinically. A complete blood count (CBC) with differential, comprehensive chemistry panel, tumor marker studies, and quality of life assessment will be performed at each follow-up interval.

We estimate that most patients will remain a subject in this study for approximately one year. Patients will remain enrolled on this protocol for a maximum of 5 years or until patient withdrawal. Patients that have completed the 5 year follow-up will continue being followed for survival information until death. The administration of subsequent chemotherapy and/or other antineoplastic treatment following Linac-based SBRT will be at the discretion of each patient's attending medical oncologist. If participants become very ill and cannot travel to IU for follow-up appointments, the study team will mail Quality of Life Questionnaires and request relevant medical records from local providers. This situation is expected due to progression profile, and if all protocol parameters are met, will not constitute a protocol deviation.

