#### Footnotes:

- Within 45 days of commencing study treatment.
- Urine or serum pregnancy test must be negative in all premenopausal women who have not undergone surgical sterilization procedures.
- FDG PET scan optional at baseline and at all follow-up intervals.
- All follow-up visits subsequent to the 4-6 week visit may be completed at an outside hospital. However, all records and imaging (copies of images in addition to reports) must be reviewed at IU. Follow-up appointments have a 30-day tolerance window. QoL surveys may be returned by mail for patients who are completing follow-up visits at an outside clinic.
- A treatment evaluation will be done in lieu of history/physical exam at these visits.
-  Surgical oncology visit note is acceptable if patient has undergone surgical procedures and is limited to travel to clinic

Protocol Version Date: 07/02/2024 Page 18

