#### 10.2 Definitions

- Duration of Response: time elapsed between SBRT completion (i.e., the last day
  of treatment) and the first sign of local progression or the development of new
  metastatic disease.
- Progression-Free Survival: time elapsed from SBRT completion to documented local/regional or distant progression or death. Local PFS will be measured as the duration from SBRT to local progression or death from any cause.
- Overall Survival: Duration from SBRT completion to patient death.

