# 11.10 Analysis of Secondary Objectives

Acute toxicities according to CTCAE 4.0 will be summarized by frequencies and rates calculated as the proportion of patients in the safety population experiencing SAEs, discontinuations due to AEs, and AEs for the two cohorts combined. For the secondary objective of estimating rates of late (> 3 months after treatment) grade 2 gastritis, enteritis, fistula, and ulcer, or any other grade 3 or greater gastrointestinal toxicity, the proportion of patients with each condition and its 90% confidence interval will be calculated.

In Cohort B only, Kaplan-Meier estimates will be used to estimate the median and 90% confidence intervals for time to local progression, overall survival, metastasis-free survival and progression-free survival. The 1-year rates and 90% confidence intervals will be also be estimated from these curves. A listing of clinical outcomes will be generated for Cohort A.

Pain control (based on reporting of standard pain score (0-10) with the option to use the FACES 0-10 scale) will be evaluated before and after Linac-based SBRT and the change in pain scores will be evaluated and summarized through descriptive statistics separately for each cohort. For Cohort B, linear mixed models will be used to model changes in pain over time. A similar approach will be used for the EORTC QOL-Q scale.

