# 11.12 Subgroup Analysis

No subgroup analyses are planned other than the separation of efficacy analyses for Cohorts A and B.

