# 15.3 Adverse Event (AE) and Serious Adverse Event (SAE) Reporting

Acute adverse events (CTCAEs) will be recorded from the time of first SBRT and for at least 90 days after treatment discontinuation, regardless of whether or not the event(s) are considered related to SBRT. All Acute AEs considered related to SBRT will be followed until resolution, return to baseline, or deemed clinically insignificant, even if this occurs post-trial.

All SAE's should be collected from the first fraction of SBRT until death or the patient enrolls in hospice. SAE's related or possibly related to study treatment or a study procedure should be reported until the patient is off study. Any death occurring within 30 days after the last fraction of SBRT or last study procedure must be reported as an SAE regardless of attribution.

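### Requiring a follow-up evaluation for the efficacy population removes early deaths from the Cohort B OS and PFS curves

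*Combined protocol and SAP*

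**What the plan says.** - **Analysis set (11.4).** The efficacy population needs eligibility, registration, at least one session of "Linac-based SBRT, and have at least one follow-up evaluation. This set will be" used for efficacy analysis. No exception is made for death. The safety population needs only one session, but it is assigned to safety analysis.
- **Estimates (11.10, 11.12).** These curves are planned for Cohort B alone: "Kaplan-Meier estimates will be used to estimate the median and 90% confidence intervals for time to local progression, overall survival". The same list names metastasis-free survival and PFS, and one-year rates are read from the curves. Section 11.12 labels the cohort-specific work as efficacy: "No subgroup analyses are planned other than the separation of efficacy analyses for Cohorts A and B".
- **Endpoints (10.2).** "Overall Survival: Duration from SBRT completion to patient death". PFS is "time elapsed from SBRT completion to documented local/regional or distant progression or death". Metastasis-free survival is not defined there.
- **Timing (7.3 and 9).** The first follow-up visit is at 4-6 weeks. Footnote 4 of the calendar adds: "Follow-up appointments have a 30-day tolerance window".
- **Patients too ill to travel (7.3).** In that case "the study team will mail Quality of Life Questionnaires and request relevant medical records from local providers".
- **Status of the estimates (3.3.2).** One-year overall, progression-free and metastasis-free survival are named secondary outcome measures.

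**The concern.** The clock for OS and PFS starts on the last day of SBRT, but entry to the analysis depends on something that happens later, namely being evaluated at follow-up. A patient who dies in between has had the event of interest, yet fails the entry condition. The curve then describes survival among those who lived long enough to be evaluated while being labelled as survival from SBRT completion. This is immortal-time selection.

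The error has a known direction. Taking an early death out of a Kaplan-Meier estimate raises the curve at every later time. The same holds for metastasis-free survival if death is an event there. At stake is the accuracy of named secondary outcome measures, which readers are likely to set beside the survival results of the earlier SBRT studies cited in section 2.2.

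**Working it through.** The plan states no target for OS or PFS, so there is no figure to reproduce. The check has two parts.

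**1. Does the text exclude these patients?** 11.4 sets the condition and ties the set to efficacy analysis. 11.10 places the OS and PFS curves in Cohort B alone, and 11.12 calls the cohort-separated analyses efficacy analyses. No section assigns these curves to the safety population, and none says that a death counts as a follow-up evaluation. The calendar in section 9 lists treatment weeks 1-2 separately from follow-up, so on-treatment checks do not naturally meet the condition. Section 10.4 provides survival follow-up for some patients who leave the study, but this does not return them to the efficacy population. On the plain reading they are excluded.

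**2. How large is the effect?** The number of deaths before any evaluation is not given, so it is assumed and varied.

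*Simple proportions, no censoring.* Inputs: about 30 Cohort B patients (11.5); 15 alive at one year, taken from the 50% one-year survival quoted for the single-fraction study in 2.2; and, for PFS, an assumed 9 of 30 event-free. With k early deaths excluded the estimate is s/(30 − k), against s/30 when all are kept.

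| k | one-year OS | one-year PFS |
|---|---|---|
| 0 | 15/30 = 50.0% | 9/30 = 30.0% |
| 1 | 15/29 = 51.7% | 9/29 = 31.0% |
| 2 | 15/28 = 53.6% | 9/28 = 32.1% |
| 3 | 15/27 = 55.6% | 9/27 = 33.3% |

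Both columns inflate by 30/(30 − k), so the lower rate moves by fewer points.

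*Constant hazard.* S(t) = exp(−ln 2 · t/m), with t in months and m the median. Conditioning on survival to the first evaluation at t0 gives S(12)/S(t0) in place of S(12). The medians are those quoted in sections 2.2 and 2.3. The cuts are 4 weeks, 6 weeks, and 6 weeks plus the 30-day tolerance (42 + 30 = 72 days, about 10.3 weeks). Each cell shows expected early deaths among 30 and the resulting one-year OS.

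| Median (source) | S(12) | 4 weeks | 6 weeks | 10.3 weeks |
|---|---|---|---|---|
| 11.4 months (single-fraction study) | 48.2% | 1.6; 51.0% | 2.4; 52.4% | 4.0; 55.7% |
| 13.8 months (five-fraction study) | 54.7% | 1.4; 57.3% | 2.0; 58.7% | 3.4; 61.7% |
| 7 months (isolated locoregional recurrence) | 30.5% | 2.6; 33.4% | 3.8; 34.9% | 6.3; 38.5% |

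With the 11.4-month median, the bias is +2.8, +4.2 and +7.5 points at the three cuts.

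*Lower early hazard.* A constant hazard probably overstates very early death, because entry requires a life expectancy above 3 months and no metastatic disease. Hold S(12) at 48.2% and scale the hazard over the first 6 weeks:

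- by one half: 4.1% die early, and 48.2/0.959 = 50.3%, or +2.1 points;
- by one quarter: 2.1% die early, and 48.2/0.979 = 49.2%, or +1.0 point.

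*Scale.* The exact (Clopper-Pearson) 90% interval for 15/30 is 33.9% to 66.1%.

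**The case against.** The best case against the point is that few patients, perhaps none, would be affected. The term follow-up evaluation is not defined, so a team might accept a death report or outside records. Section 7.3 allows more frequent visits when clinically indicated, so a patient who deteriorates may well be seen before the scheduled visit. Footnote 6 of the calendar accepts a surgical oncology note for the 4-6 week visit in some patients. Entry requires Karnofsky status above 70%, life expectancy above 3 months and no metastatic disease. The estimates are secondary and descriptive, in a pilot focused on safety, and early deaths would appear in the disposition table (11.8).

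Much of this stands as a limit on size. Very ill living patients may still qualify, and zero exclusions among about 30 patients is plausible. It does not remove the fault. The text does not say that a death counts as an evaluation, and leaving that to be decided once the deaths are known is undesirable. A disposition table shows the excluded deaths but does not correct the curve. The link from 11.10 to the efficacy population is an inference through 11.12, but no other analysis set is offered for these curves.

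A further objection is that a patient who stops SBRT early may have no clear time origin. That problem already exists under the current set, which also needs only one session. Section 10.2 largely answers it by equating completion with the last day of treatment.

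**Conclusion.** The concern holds. As written, a treated Cohort B patient who dies before any follow-up evaluation is left out of the OS and PFS curves, and each such exclusion moves the estimates upward. Under the assumptions of 30 patients and 50% one-year survival, one to three excluded deaths add 1.7 to 5.6 points to one-year OS. If the early hazard is a quarter to a half of the constant-hazard value, as the entry criteria make plausible, the bias is about 1 to 2 points. It is zero if nobody dies unevaluated.

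These sizes rest on an early-death rate that the documents do not supply and on survival figures from other regimens and populations; only the direction is certain. The bias is smaller than the sampling error. No hypothesis test depends on these estimates, and the primary safety endpoint and stopping rule are untouched. It is a change that should be made, chiefly because the bias is one-sided and easily avoided.

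**What to change.** 1. In 11.4 and 11.10, analyse OS, PFS and metastasis-free survival in all Cohort B patients who received at least one SBRT fraction. This is the safety population already defined, or its eligible subset if the sponsor wishes to keep the eligibility condition.
2. Count deaths before the first evaluation as events for OS and PFS. Do the same for metastasis-free survival once 10.2 defines it with death as an event.
3. Censor other patients at the date last known alive (OS) or last known event-free (PFS, metastasis-free survival).
4. State that, for the time origin, completion means the day of the last fraction received, so that patients who stop early have a start date.
5. Keep the follow-up condition only for response, pain and quality of life. Report how many treated patients had no evaluation, and why.

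The cost is wording in the analysis plan. Section 11.1 requires no protocol amendment unless a significant feature changes. The data should largely exist: section 15.3 already requires reporting of "Any death occurring within 30 days after the last fraction of SBRT" and collects serious adverse events until death or hospice entry. For deaths after hospice entry, the sponsor should confirm that the date is recorded. Reported survival may be slightly less favourable.
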